### **Standard Research Summary**

**Purpose of the Study** 

Objectives & hypotheses to be tested

We propose to assess the relative role of nicotine dose and route of delivery in affecting successful switching from combustible cigarettes to e-cigarettes, as well as concomitant reductions in *ad libitum* cigarette smoking and exposure to harmful and potentially harmful constituents of combustion.

The strategy will be to assess adoption of e-cigarette use and concomitant reduction in *ad libitum* smoking of subjects' usual brands of cigarettes over an 8-week period, during which they will receive nicotine or non-nicotine e-cigarettes, and nicotine or non-nicotine skin patches. The nicotine patches will not be used as a therapeutic treatment in this study, but rather as a way to manipulate the nicotine dose, while varying the rate and route of nicotine delivery. Behavioral or "habit" aspects of e-cigarette use will be controlled for by the groups receiving non-nicotine e-cigarettes.

We hypothesize that e-cigarette use will be higher, and concomitantly, combustible cigarette use will be lower, in the nicotine e-cigarette condition compared to the zero-nicotine e-cigarette condition (i.e., comparing Group 1 vs. Group 2).

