Although subjects receiving nicotine from e-cigarettes will no doubt receive a range of nicotine doses, depending on the extent of use, data from previous studies (Shahab et al., 2017) suggests that the mean dose is expected on average to be similar to that provided by a 21 mg/day patch (and actual mg/day, as estimated from the number of e-liquid cartridges consumed, will be a covariate in the statistical analyses.).

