### Design Overview

The study will comprise a randomized, double-blind parallel-arm study to ascertain the role of nicotine dose and route of administration in reducing use of combustible cigarettes and in facilitating adoption of e-cigarettes. One hundred thirty daily cigarette smokers will be randomly assigned to receive 8 weeks of exposure to the following conditions (65/group):

- 1. Nicotine containing e-cigarettes + 21 mg nicotine skin patches
- 2. Zero-nicotine e-cigarettes + 21 mg nicotine skin patches

Nicotine and non-nicotine e-cigarettes will be purchased from JUUL Labs. The JUUL is a rectangular closedsystem e-cigarette. This e-cigarette was commercially available as of August 8, 2016 and does not contain any alterations to the chemistry or physical characteristics. Each JUUL Pod pack contains 4 pods. Each JUUL Pod contains 0.7mL with 5% nicotine by weight, approximately equivalent to one pack of cigarettes or 200 puffs. Multiple flavors will be used in this study in order to more accurately mimic real world conditions. Subjects will receive packs containing tobacco-flavored and mint-flavored or menthol-flavored pods. Subjects will be provided with enough additional packs of pods to use during the smoking period. JUUL Pods are sealed system cartridges for use in the JUUL e-cigarette. Each pod is contained in tamper resistant blister packs. The nicotine patches will be purchased from Duke Outpatient Pharmacy.

Ad libitum smoking will be assessed weekly using daily diary recordings of cigarettes smoked per day as well as the objective index of expired air carbon monoxide (CO) levels measured at the study visits.

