### **Data Analysis & Statistical Considerations**

 Describe endpoints and power calculations. Provide a detailed description of how study data will be analyzed, including statistical methods used, and how ineligible subjects will be handled and which subjects will be included for analysis. Include planned sample size justification. Provide estimated time to target accrual and accrual rate. Describe interim analysis including plans to stop accrual during monitoring. Phase I studies, include dose escalation schema and criteria for dose escalation with definition of MTD and DLT.

The primary outcome measures will be the amount of combustible cigarette use and e-cigarette use in the last week of the 8-week exposure period. The main index of combustible cigarette use will be expired air CO, a highly sensitive and specific measure of smoke inhalation. As a secondary measure (at the first (V1) and final (V5) sessions), we will assess total urinary 4-(methylnitrosamino)-1-(3-pyridyl)-1-butanol (NNAL), a metabolite of the tobacco-specific carcinogen 4-(methylnitrosamino)-1-(3-pyridyl)-1-butanone (NNK). The half-life of NNAL is 10 days (Goniewicz et al., 2009), yielding a valuable index of sustained reductions in cigarette smoking. The half-life of expired air CO, in contrast, is 4.5 h (Sandberg et al., 2011).

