Self-reported cigarettes/day recorded on diaries will also be a secondary index of cigarette consumption. The main index of e-cigarette use will be the number of cartridges consumed, based on selfreport and counts of the number of unused e-cigarette tanks returned. We hypothesize that e-cigarette use will be higher, and concomitantly, combustible cigarette use will be lower, in the nicotine e-cigarette condition compared to the zero-nicotine e-cigarette condition (i.e., comparing Group 1 vs. Group 2). This hypotheses will be evaluated using General Linear Modeling (GLM) techniques to assess the significance of the nicotine factor, using a 1-tailed alpha=0.05. A one-tailed comparison is justified given that a higher dose of nicotine in the e-cigarette would only be expected to decrease use of conventional cigarettes. Moreover, there would be no interest in pursuing the nicotine e-cigarette plus nicotine patch combination if it led to greater smoking than the placebo e-cigarette plus nicotine patch. Thus, the 5% Type I error rate can reasonably be assigned to the 1-tailed comparison. Covariates in the analysis of combustible cigarette use will include the amount of e-cigarette use, since that will affect the overall dose of nicotine received by subjects, as well as baseline combustible cigarette use, and baseline demographic and smoking history variables (the latter will also serve as covariates in the analysis of e-cigarette use as a dependent measure). We predict at least a moderate effect size (0.5) for each of the main effects, nicotine and route of administration, so that a sample size of 50 per group will yield at least 80% power to detect the hypothesized effects.

• Summarize safety concerns, and describe the methods to monitor research subjects and their data to ensure their safety, including who will monitor the data, and the frequency of such monitoring. If a data monitoring committee will be used, describe its operation, including stopping rules and frequency of review, and if it is independent of the sponsor (per 45 CFR 46.111(a) (6)).

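### The primary model for combustible cigarette use adjusts for e-cigarette use, a post-randomisation co-primary outcome on the hypothesised pathway, so its group term no longer estimates the trial's effect

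*Combined protocol and SAP*

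**What the plan says.** The section Data Analysis & Statistical Considerations names two primary outcomes: "The primary outcome measures will be the amount of combustible cigarette use and e-cigarette use in the last week of the 8-week exposure period". Expired air CO is the main index of the first, and cartridges consumed is the main index of the second.

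The hypothesis, given under Purpose of the Study and repeated in the analysis section, is that "e-cigarette use will be higher, and concomitantly, combustible cigarette use will be lower, in the nicotine e-cigarette condition" than in the zero-nicotine condition. It is tested through the nicotine factor in a general linear model, "using a 1-tailed alpha=0.05".

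On adjustment, the analysis section says: "Covariates in the analysis of combustible cigarette use will include the amount of e-cigarette use". The reason given is that e-cigarette use affects the total nicotine dose. The other listed covariates (baseline combustible use, demographics, smoking history) are all pre-randomisation. Background & Significance gives the same adjustment in dose form: "actual mg/day, as estimated from the number of e-liquid cartridges consumed, will be a covariate in the statistical analyses".

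The plan specifies no analysis of combustible use without this covariate, and it does not label the adjusted model a mediation, direct-effect or sensitivity analysis.

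**The concern.** The trial asks whether putting nicotine in the e-cigarette makes smokers vape more and therefore smoke less. The Research Abstract and the Risk/Benefit Assessment both say that exposure may fall to the extent that e-cigarettes take the place of cigarettes. The documents do not use the word mediator, but that is what they describe.

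Conditioning on the mediator has two consequences.

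- The group coefficient becomes the arm difference among people with equal e-cigarette use. Any benefit gained by vaping more is subtracted out, although that is the benefit the hypothesis predicts.
- E-cigarette use is not randomised. Comparing arms at equal use mixes in any unmeasured cause of both vaping and smoking, such as dependence. Randomisation no longer protects the comparison.

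The dose rationale does not justify the adjustment. Pods in Group 2 contain no nicotine, so their cartridge count does not measure dose. In mg/day form every Group 2 participant has the value zero. The covariate is then strongly tied to group, and the group term becomes the arm difference extrapolated to zero e-cigarette nicotine.

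Followed as written, a trial in which nicotine e-cigarettes work as hypothesised could report no effect on smoking, and a trial with no effect could report a benefit.

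**Working it through.** **Inputs from the documents**

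- One-sided alpha 0.05: "using a 1-tailed alpha=0.05".
- Standardised effect 0.5: "We predict at least a moderate effect size (0.5) for each of the main effects, nicotine and route of administration".
- Stated power: "a sample size of 50 per group will yield at least 80% power to detect the hypothesized effects".
- Randomised size (Design Overview): "One hundred thirty daily cigarette smokers will be randomly assigned to receive 8 weeks of exposure to the following conditions (65/group").

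**Inputs assumed, because the documents do not give them**

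- *a*: arm difference in e-cigarette use, in within-arm SDs; range 0.3 to 1.0.
- *r*: within-arm correlation of e-cigarette use with CO; 0 to -0.5 for substitution, positive for a shared cause.
- Coefficient of variation (CV) of nicotine mg/day in Group 1: 30% to 80%.

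**Step 1: reproduce the stated power.** Without the covariate, the noncentrality is 0.5 / √(2/n).

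- n = 50: 0.5 / 0.2 = 2.50, power 79.9% (noncentral t, df 98).
- n = 65: 2.85, power 88.3%.

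The 80% claim is therefore for the total group difference, without e-cigarette use in the model.

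**Step 2: the planned model.** Let T be the total effect on CO in SDs, here -0.5. With e-cigarette use in the model:

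- group coefficient = T − a·r
- SE = √[(1 − r²)(2/n)(1 + a²/4)]
- df = 2n − 3

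Example with a = 1, r = -0.25, n = 50: the coefficient is -0.5 + 0.25 = -0.25. The SE is √(0.9375 × 0.04 × 1.25) = 0.2165. The ratio is -1.155 and power is 31%.

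| a | r | share of effect removed (a·r/T) | coefficient | power, 50/group | power, 65/group |
|---|---|---|---|---|---|
| 0.5 | 0 | 0% | -0.50 | 78% | 87% |
| 0.3 | -0.2 | 12% | -0.44 | 71% | 81% |
| 0.5 | -0.25 | 25% | -0.375 | 59% | 69% |
| 0.5 | -0.3 | 30% | -0.35 | 55% | 65% |
| 0.5 | -0.5 | 50% | -0.25 | 40% | 48% |
| 1.0 | -0.25 | 50% | -0.25 | 31% | 37% |
| 1.0 | -0.5 | 100% | 0.00 | 5% | 5% |

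Simulation with 4,000 replicates per setting agrees. At 50 per group it gave 55.5% (a = 0.5, r = -0.3), 40.1% (a = 0.5, r = -0.5) and 4.9% (a = 1, r = -0.5), against about 80% without the covariate.

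**Step 3: no true effect on CO (T = 0).** Let one shared cause load 0.5 on both measures, so r = 0.5 × 0.5 = +0.25. At 50 per group:

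- a = 0.5: coefficient -0.125, SE 0.1996, ratio -0.626, one-sided rejection rate 15%.
- a = 1: coefficient -0.25, SE 0.2165, ratio -1.155, rejection rate 31%.

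The nominal rate is 5%.

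**Step 4: the mg/day form.** Group 2 is all zero. Take the Group 1 mean as 21 mg, following the plan's expectation that average intake resembles the patch; the mean cancels. The between-arm variance of the covariate is mean²/4 and the pooled within-arm variance is (CV × mean)²/2. The variance inflation of the group term is therefore 1 + 1/(2·CV²).

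- CV 30%: 1 + 1/0.18 = 6.56. Ratio 2.5/√6.56 = 0.976, power 25% at 50 per group.
- CV 80%: 1 + 1/1.28 = 1.78. Ratio 2.5/√1.78 = 1.87, power 59% (58.5%).

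This loss occurs even when none of the effect is mediated. Simulation gave similar values: inflation of about 2 to 7 and power of roughly 25% to 55%.

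**The case against.** The strongest reply concedes the change of estimand and disputes its size.

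- **Size.** The worst figures need a 1 SD arm difference in e-cigarette use, whereas the only planning effect size in the documents is 0.5. With a = 0.3 and r = -0.2, power is still 71% or 81%. This stands: the loss is a range, and full mediation is its extreme.
- **False positives.** The plan also adjusts for baseline combustible use and smoking history, which partly capture dependence. In a simulation at 50 per group, adding a baseline proxy correlated 0.7 with the shared cause lowered the rejection rates from 14% and 29% (a = 0.5 and 1) to 9% and 17%. A proxy correlated 0.85 lowered them to 7% and 11%. This also stands: the inflation shrinks but does not vanish. The test does hold 5% for its own null, no adjusted difference, but that is not the stated hypothesis.
- **The mg/day text.** It sits in the background section and may survive from an earlier design; Selection of Subjects still mentions four conditions. The analysis section refers to amount of use, indexed by cartridges, which is not zero by construction in Group 2. This is fair, so mg/day is a secondary point, but both statements are in the current document.
- **Intent.** The objective concerns nicotine dose and route, and a dose-adjusted contrast may inform that. It can do so as a separate analysis under an assumption of no unmeasured common causes. It cannot stand in for the randomised Group 1 versus Group 2 comparison.

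**Conclusion.** The concern holds and must be fixed, because it affects the primary test of combustible use. The group coefficient misses the total effect unless e-cigarette use is the same in both arms, which contradicts the trial's hypothesis, or is unrelated to CO within arm, which contradicts its substitution rationale. That conclusion needs no assumed values.

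The size does. For a total effect of 0.5 SD at 50 per group, power falls from 80% to between 71% and 31% over arm differences of 0.3 to 1 SD and within-arm correlations of -0.2 to -0.3 as tabulated, and to 5% under full mediation. With no true effect, positive shared causation raises the one-sided error rate to 15% to 31% before baseline proxies are considered, and less with good ones. The direction of the bias depends on the sign of the within-arm correlation, which the documents do not give. The 80% power statement applies to a model that the plan does not specify.

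**What to change.** In Data Analysis & Statistical Considerations, define the primary model for expired CO as group, baseline CO, and the named pre-randomisation demographic and smoking-history covariates. Remove amount of e-cigarette use from it, and remove or redirect the mg/day covariate sentence in Background & Significance.

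If the dose or switching question is wanted, put e-cigarette use and mg/day in a separately labelled exploratory mediation analysis. State there the assumption of no unmeasured common causes of vaping and smoking, and that mg/day is zero throughout Group 2. E-cigarette use remains a primary outcome in its own model.

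The change is wording only and needs no new data. It restores the contrast to which the power statement applies: 79.9% at 50 per group and 88.3% at 65 per group, before any gain from baseline adjustment.

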### Sessions

The first study visit (V1) will take place approximately one week after the screening visit. Subjects will complete baseline questionnaires and will be randomized to one of the two groups. Subjects will be tested for exhaled air carbon monoxide, and saliva samples will be collected for analysis of smoking related chemicals (e.g., cotinine). Subjects will also complete questionnaires assessing their dependence on cigarettes (Fagerström Test for Nicotine Dependence (FTND) (Heatherton et al., 1991)), and rewarding effects of cigarettes (modified Cigarette Evaluation Questionnaire (Cappelleri et al., 2007)).

Subsequent study visits will occur approximately two weeks apart (with a five-day window on either side of the scheduled visit). If a participant does not attend a visit and it cannot be rescheduled within the allowable window, the visit will be considered a missed visit; if participants miss two consecutive visits they will be withdrawn from the study. Participants will be tested for exhaled air carbon monoxide, and will also complete questionnaires assessing their dependence on cigarettes (Fagerström Test for Nicotine Dependence (FTND) (Heatherton et al., 1991)), and rewarding effects of cigarettes (modified Cigarette Evaluation Questionnaire (Cappelleri et al., 2007)).

Questionnaires will be completed within REDCap on a desktop computer in the Center office. The technician will log on to the REDCap site and will open the questionnaires for the subjects. Subjects will only have access to their questionnaires. Access to any other websites will be blocked by Duke Psychiatry Information Technology.

At the first (V1) and final (V5) sessions, participants will provide saliva and urine samples. The saliva sample will be used for analysis of smoking related chemicals (e.g., cotinine). The urine sample will be used to assess total urinary 4-(methylnitrosamino)-1-(3-pyridyl)-1-butanol (NNAL), a metabolite of the tobacco-specific carcinogen 4-(methylnitrosamino)-1-(3-pyridyl)-1-butanone (NNK). The half-life of NNAL is 10 days (Goniewicz et al., 2009), yielding a valuable index of sustained reductions in cigarette smoking. The half-life of expired air CO, in contrast, is 4.5 h (Sandberg et al., 2011). Total urinary nicotine equivalents (a measure of total nicotine intake) will also be assessed.

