### Remote Study Participation

Potential subjects who live in North Carolina but do not live close enough to travel to our Center will be able to participate in the study remotely. Interested individuals will complete the online REDCap initial screening survey and provide contact information. The responses of potential participants who agree to be in the study will be reviewed by study staff who will then contact eligible respondents by phone to answer any questions and explain how to electronically sign and date the e-consent form. A PDF copy of the signed consent form will be emailed to participants. Participants will then report to a LabCorp facility close to them to provide a urine sample to test for illegal drugs and pregnancy (for females of child bearing potential). If the urine tests are negative, participants will be sent a CO monitor for measuring carbon monoxide (CO), and study e-cigarette and nicotine patches. Participants will complete surveys (asking about potential side effects, mood, and experiences with the e-cigarettes, patches and their usual brand cigarettes) at five time points, once every 2 weeks, and at follow-up 4 weeks after stopping the use of study e-cigarettes and patches. CO readings will be obtained at screening and evisit 5.

Electronic Screening Survey: Interested individuals will respond to various advertisement strategies (television, social media advertisement, etc.) by completing a public online REDCap screening survey. After reading a brief description of the study in the survey, interested potential participants will complete questions regarding smoking and medical history in order to assess safety and eligibility for participation in the study. Potential participants will be deemed ineligible if they decline to complete the initial online screening survey, fail to leave their contact information, or do not meet eligibility criteria based on survey responses. Eligible individuals interested in participating will be contacted via phone by study personnel to discuss the process of remote e-consent.

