Randomization and E-cigarette Distribution: After the 1-week training/baseline period is complete and any concerns or questions about the CO monitoring have been addressed, the participants will be assigned a participant number that will determine their randomly assigned study condition, and will be sent by study staff the first shipment of study patches and e-cigarette devices and cartridges containing e-liquid corresponding to their group assignment (nicotine containing e-cigarettes vs. zero-nicotine e-cigarettes). Packages containing nicotine patches and e-cigarettes and liquids require signature by someone who is 21 years of age or older for delivery; the packages will not be delivered if no one appropriate is available to sign for them. This supply will be designed to last through the first 4 weeks of the study; if participants remain in the study, they will be sent a second shipment to use for the final 4 weeks.

Study Milestones: Remote participants will complete study milestones ("e-visits") that correspond to the study visits attended by local participants: baseline, week 2, week 4, week 6 and week 8, plus 4-week follow-up; they will take approximately one hour each to complete and include the same questionnaires that are completed at the in-person study visits, as well as a CO measurement at e-visit 5. The first (baseline) study milestone (V1) will take place after the participants receive their first shipment of e-cigarettes but before they start using them. At this time, participants will be called by study staff and given instructions on how to use the e-cigarettes. They will be asked to switch from cigarette use to use of e-cigarettes during the study. They will then be instructed on the use of daily self-report diaries to be completed on paper. In these diary entries, participants will record the number of conventional cigarettes smoked each day and the number of occasions of e-cigarette use (an occasion defined as taking at least one puff). Participants will be emailed a survey link to complete the questionnaires online via REDCap. Participants will have 72 hours to complete the survey until it expires and it is considered a "missed milestone"; if participants miss two consecutive milestones they will be withdrawn from the study. The

diary entries will be reported to the research staff by phone after e-visit online surveys have been completed.

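### Participation mode (in-person or remote) is not listed in the analysis models: a possible small loss of precision for CO and NNAL, and for e-cigarette use a measurement mismatch that a mode term alone cannot repair

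*Combined protocol and SAP*

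**What the plan says.** Data Analysis & Statistical Considerations tests the nicotine factor in a general linear model "using a 1-tailed alpha=0.05". The covariates for combustible cigarette use are the amount of e-cigarette use "as well as baseline combustible cigarette use, and baseline demographic and smoking history variables". The demographic and smoking history variables also enter the model for e-cigarette use. Participation mode is not named as a covariate, stratification factor or subgroup in any section, and no separate analysis of remote participants is described.

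The procedures differ by mode in three respects:

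- **CO.** In-person participants have CO measured at screening, at V1 ("Subjects will be tested for exhaled air carbon monoxide, and saliva samples will be collected") and at each later visit. For remote participants, "CO readings will be obtained at screening and evisit 5". The paragraph on return and re-use of the monitor agrees: the monitor goes back after screening and is sent again for e-visit 5.
- **E-cigarette use.** The main index is cartridges consumed. Under Sessions, in-person diaries record cartridges, and pods are brought back at the next visit. Under Remote Study Participation, the diary records "the number of occasions of e-cigarette use (an occasion defined as taking at least one puff"; entries are reported by phone, and no return of pods is described.
- **Contact and supply.** In-person participants attend every two weeks. Remote participants have online surveys, phone contact and two shipments.

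Remote participants are "assigned a participant number that will determine their randomly assigned study condition". Nothing states that the list is blocked or stratified by mode.

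**The concern.** Mode is settled before a participant number is issued, so it is a legitimate baseline factor. Procedures that differ by mode could give the two groups different outcome levels. If so, a model without mode leaves that difference in the residual error and widens the interval for the arm contrast. The protocol's power calculation uses 50 per group and has no margin at that number, so even a modest increase in variance takes power below the stated 80%.

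Two related matters depend on mode. The baseline smoking covariate is not tied to a visit, and remote participants have no V1 CO. E-cigarette use, a primary outcome and also a covariate in the combustible-use model, is recorded in different units in the two modes.

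**Working it through.** **Inputs from the documents.** One-sided alpha 0.05; standardised effect 0.5 ("We predict at least a moderate effect size (0.5) for each of the main effects"); "a sample size of 50 per group will yield at least 80% power to detect the hypothesized effects"; 65 per group to be randomised (Design Overview).

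**Assumptions.** The documents do not give the remote share p or the mode difference D, in within-mode SDs. Take p = 0.2 to 0.5 and D = 0.3 to 0.8, where D is what remains after the planned covariates. D = 0 is also possible. The 0.5 effect is taken on the within-mode SD.

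**Step 1: the plan's own figure.** The normal approximation for two means, one-sided 0.05, gives n = 50 per group and power 80.4%. The noncentral t gives 79.9% at 50 per group and 88.3% at 65. The stated figure is reproduced. The noncentral t is used from here on.

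**Step 2: variance inflation.** Omitting a two-level factor with share p and effect D multiplies the residual variance by 1 + p(1-p)D².

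- p = 0.2, D = 0.3: 1 + 0.16 × 0.09 = 1.0144
- p = 0.5, D = 0.8: 1 + 0.25 × 0.64 = 1.16

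**Step 3: power.** The effective standardised effect is 0.5/√(inflation).

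| p, D | Inflation | Effective effect | Power, 50/group | Power, 65/group |
|---|---|---|---|---|
| any, 0 | 1 | 0.500 | 79.9% | 88.3% |
| 0.2, 0.3 | 1.014 | 0.496 | 79.4% | 87.9% |
| 0.5, 0.8 | 1.160 | 0.464 | 74.5% | 83.8% |

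The loss is 0.5 to 5.4 points at 50 per group and 0.4 to 4.5 points at 65 per group.

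**Step 4: bias and error rate.** These were simulated with 8,000 runs per setting, half of participants remote and a true effect of 0.5. The mean estimate was 0.50 with and without the mode term. With unstratified allocation, Type I error stayed near 0.05 either way. With allocation balanced by mode, D = 1.0 and the term omitted, Type I error fell to about 0.03, so the test became conservative. A list blocked by mode should therefore be paired with a mode term in the model.

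**Step 5: baseline CO.** Before treatment, in-person participants have screening and V1 readings, and remote participants have screening only. Screening CO is the only pre-treatment reading described for both.

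**Step 6: e-cigarette use.** The formula in Step 2 presumes one outcome scale. Cartridges and occasions of use are not on one scale, and a mode intercept shifts level without converting units. As a covariate, the mixed measure would also need a different slope in each mode. The calculation above therefore applies to CO and NNAL only. It also sets aside the separate question of adjusting for e-cigarette use, which is measured after randomisation.

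**The case against.** The size of the harm is assumed. With no mode effect there is no loss, and planned baseline smoking, demographic and smoking history covariates may absorb part of any mode difference. Even the largest loss above leaves 83.8% power if all 65 per group are analysed. All of this stands, and it is why the point is minor. It does not remove the case for a term that costs one degree of freedom.

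The 0.5 effect may be meant on the overall SD. The planned power would then already contain the mode variance, and omitting mode would forgo a gain instead of causing a fall. For p = 0.5 and D = 0.8 at 50 per group, the normal approximation rises from 80.4% to 85.3% once mode is included. The documents do not settle the scale, but the recommendation is the same on either reading.

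Both modes have CO at V5 or e-visit 5, and remote readings are observed over Zoom. The extra in-person interim readings do not enter the last-week outcome. That is correct, so for CO the recorded differences concern baseline timing and contact, not whether the outcome is available.

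The covariate list may not be closed, and pooling is inferred from silence. That is also fair. It argues for naming mode now, because adding it after seeing the data would be a post hoc choice.

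Three stronger readings are tempting but not supported:

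- **A reader might infer that remote participants will drop out of the analysis for want of a V1 CO.** The plan ties baseline smoking to no visit, so this follows only if V1 CO is chosen and complete covariates are required.
- **A reader might count chance imbalance of mode between arms as a second harm.** Its 95% limit at 65 per group is 1.96 × D × √(2p(1-p)/65), or 0.041 to 0.138 SD. But the added variance of the contrast, 2p(1-p)D²/65, is the same quantity already in the inflation and the power loss.
- **A reader might infer bias.** Mode precedes randomisation, and the simulation shows none.

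**Conclusion.** The concern holds as a minor precision point. The models do not list mode, mode is known before randomisation, and procedures differ by mode. Omitting it does not bias the arm comparison. The loss is zero if mode has no effect, and about 0.5 to 5 power points under the assumed 20-50% remote share and a 0.3-0.8 SD mode difference remaining after the planned covariates. In that range power stays above 80% at 65 per group. At 50 per group it falls just below 80% in the mildest case and to 74.5% in the worst.

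For e-cigarette use the difficulty is measurement before it is precision: the main index is cartridges, and the remote diary as described does not record them.

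**What to change.** 1. **CO and NNAL models.** Add participation mode as a two-level factor. This costs a sentence of analysis text and one degree of freedom, using data already held.
2. **Allocation.** If it is still open, block the list within mode. This changes only the list, and the mode term should then be kept in the model.
3. **Baseline CO.** Name screening CO as the baseline CO covariate for everyone. The small downside is that the later in-person V1 reading goes unused, and screening CO is truncated at the 10 ppm entry limit, so some in-person precision may be given up.
4. **E-cigarette use, as outcome and as covariate.** First reconcile the in-person diary and pod-return text under Sessions, the remote diary text under Study Milestones, and the definition of the main index, so that cartridges consumed is obtained in both modes. For example, remote participants could also report cartridges used. Then add mode to that model. This step is not analysis wording alone: it needs an extra item in remote data collection, and a stated rule for any remote participants who have already finished without it.
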